### **6.2 Recording of adverse events**

AE will be collected by means of a standard question: “Have you had any health problems since the previous visit?” Reported AE’s and/ or observed AE’s will be recorded on the AE Form. The AE Forms will be stored in Investigator's Study File.

#### **6.1.1 Time period for collection of adverse events**

AE and SAE will be analyzed at each visit during index hospitalization and at the last visit at 6-months.

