### **3.9 Discontinuation of investigational product**

The investigational product (IP) may be discontinued at any time at the discretion of the PI or the study subject. Criteria for discontinuing the investigational product include:

- Withdrawal of informed consent.
- Development of exclusion criteria, pregnancy or other safety reasons during the study (requirement of unacceptable concomitant medication, adverse event, intolerance of the IP)
- Protocol non-compliance.
- Incorrect enrolment or randomization of the subject.

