#### **4. STUDY PLAN AND TIMING OF PROCEDURES**

Visit	1	2	3	4	5	No follow-up	For details see Protocol Section
Visit window							
Day -1 to 0 for Visit 1							
±1 day for Visit 2							
±3 days for Visit 3							
±5 days for Visit 4							
± 6 months for Visit 5							
Week		0	1			24	
Day	-	0	1	3	5	168	
Written informed consent	X						
Demographics	X						
Physical examination, height, and weight	X		X	X	X	X	

Visit	1	2	3	4	5	No follow-up	For details see Protocol Section
Visit window							
Day -1 to 0 for Visit 1							
±1 day for Visit 2							
±3 days for Visit 3							
±5 days for Visit 4							
± 6 months for Visit 5							
Week		0	1			24	
Day	-	0	1	3	5	168	
Medical/surgical history	X						
Inclusion/exclusion criteria	X	X					
12-lead ECG	X		X	X	X	X	
Vital signs	X	X	X	X	X	X	
Randomisation to study treatment		X					
Treatment dispensed/returned		X				X	
Concomitant medication	X	X	X	X	X	X	
Adverse event review (AEs and SAEs)		X	X	X	X	X	

Visit	1	2	3	4	5	No follow-up	For details see Protocol Section
Visit window							
Day -1 to 0 for Visit 1							
±1 day for Visit 2							
±3 days for Visit 3							
±5 days for Visit 4							
± 6 months for Visit 5							
Week		0	1			24	
Day	-	0	1	3	5	168	
Blood samples for haematology and clinical chemistry	X			X		X	
Urinalysis	X			X		X	
Blood sampling for pharmacokinetics		n.a.	n.a.	n.a.	n.a.	n.a.	

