## 6.1.3 Variables

The following variables will be collected for each AE;

- Description of AE.
- The date and time when the AE started and stopped.
- The intensity of the AE according as assessed by study subjects according to the following scale:
  - Mild = awareness of sign or symptom, but easily tolerated
  - Moderate = discomfort sufficient to cause interference with normal activities
  - Severe = incapacitating, with inability to perform normal activities.
- The intensity of the AE assessed by PI as CTCAE grade 1-5.
- Whether the AE is serious or not. The AE assessed by the study subject as severe AE is not equivalent to serious AE.
- Causality assessment in relation to study treatment.
- Action taken with regard to investigational product.
- Withdrawal of the subject from the study due to AE.
- Outcome.

In addition, the following variables will be collected for SAEs:

- Date when AE met criteria for serious AE.
- Date Investigator became aware of serious AE.
- The reason why AE is serious.
- Date of hospitalization.
- Date of discharge or death.
- Probable cause of death.
- Autopsy performed.

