### **10.4 Informed consent**

The PI will inform every subject in detail about the nature of the study, its purpose, the treatments and the probability of random assignment to treatment groups. Every subject will receive information sheet and provide written informed consent prior to participation the study. A copy of the Patient Information Sheet and signed Consent Form will be given to the subject. The original will be stored by the PI in the Investigator's Study File. A sample of the

Patient Information Sheet and Consent Form can be found in the Appendix C of this protocol (in Polish). The study subjects will also be informed that:

- Participation in this study is voluntary and the informed consent to participate in the study may be withdrawn at any time for any reason, and that withdrawal of consent will not affect the subsequent medical treatment or relationship with the treating physician.
- They will be notified if information becomes available that may be relevant to their willingness to continue participation in the study.
- They will be notified if alternative treatment becomes available, as well as about the potential benefits and risks of this alternative treatment.
- They will be strongly encouraged to contact the PI to report on any potentially study-related adverse events, as well as for further information regarding the study.

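### Solicited adverse-event collection has a gap of about 163 of 168 treatment days; a fixed checklist at the existing 6-month visit would reduce the risk of missed non-serious events

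*Combined protocol and SAP*

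**What the plan says.** Section 6.1.1 sets the times of review: "AE and SAE will be analyzed at each visit during index hospitalization and at the last visit at 6-months". The Section 4 schedule agrees. Its AE review row is marked at Days 0, 1, 3, 5 and 168, with nothing between the last two.

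Section 6.2 (Recording of adverse events) gives the method, one standard question: "Have you had any health problems since the previous visit". It adds: "Reported AE’s and/ or observed AE’s will be recorded on the AE Form". For each event, Section 6.1.3 requires, among other items, "The date and time when the AE started and stopped".

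Between visits, Section 10.4 relies on the subject: "They will be strongly encouraged to contact the PI to report on any potentially study-related adverse events". Section 6.4.1 separately instructs female subjects to tell the investigator of a pregnancy. Section 3.9 makes "Development of exclusion criteria, pregnancy or other safety reasons during the study" a ground for stopping the investigational product.

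The design is open-label for subjects, while Section 3.6 states that the principal investigator is blinded. Sections 2.3 and 8.3.2 say that safety is compared between the arms descriptively.

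**The concern.** The safety objective sets ticagrelor against clopidogrel, and AEs are to be listed by arm. Almost all treatment time falls after discharge, where nobody asks about events until the end. At that point one unprompted question has to cover nearly half a year, and the AE Form still needs start and stop times. An event that came and went, such as a minor bleed or an episode of breathlessness, is easily left out of the answer.

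The between-visit route is narrower than the protocol's own AE definition. Section 6.1 counts an event whether or not the drug caused it, whereas Section 10.4 invites reports of events that might be related to the study. The subject applies that filter knowing the assigned drug. If subjects in one arm expect more side effects, they may report more of them.

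Timeliness is also at stake. The 24-hour rule in Section 6.2 (Reporting of serious adverse events) applies to events documented on the SAE Form, so a post-discharge admission that nobody mentions starts no clock.

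**Working it through.** **Inputs.** Last in-hospital AE review: Day 5 (Section 4). Final visit: Day 168 (Section 4), which matches the 24 weeks of drug in Section 7.5, 24 × 7 = 168. No follow-up after treatment (Section 4.3). Drug is dispensed once, and compliance is checked only at 6 months (Sections 4 and 7.5), so no interim contact arises for another reason. The plan states no AE rate, recall figure or safety precision, so there is no safety figure of its own to reproduce.

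**Share of treatment days without a scheduled AE contact** = (final day − last early contact) / final day.

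| Last early contact | Final day | Gap (days) | Share |
|---|---|---|---|
| Day 5 (nominal) | 168 | 163 | 97.0% |
| Day 3 | 168 | 165 | 98.2% |
| Day 10 (Day 5 plus the 5-day window) | 168 | 158 | 94.0% |
| Day 5 | 183 (6 calendar months) | 178 | 97.3% |

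The schedule table is partly broken in the text available (five visits, six day columns), hence the range. The window for Visit 5 is printed as plus or minus 6 months. Read literally, that leaves the length of the recall period open and needs to be reconciled with Day 168.

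**What crosses the gap.**

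- *Section 10.4 self-report:* passive, and limited to events the subject links to the study.
- *Section 6.4.1 pregnancy self-report:* a specific instruction, for that one event.
- *Day 168 examination, ECG, vital signs, laboratory tests and urinalysis (Section 4; safety listing in 8.3.2):* these mainly show status on the day. An event that has resolved may leave no trace.
- *Day 168 concomitant-medication review (Section 4):* may reveal an event through a new drug, but again by recall.
- *Symptom questionnaire by organ system (Sections 5.3.1 and 8.3.4):* a structured prompt, but it has no visit times, is absent from the schedule and is not linked to the AE Form.

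None of these is a scheduled AE enquiry between Day 5 and Day 168.

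**Illustration, on assumptions that are not in the documents.** Take 30 subjects per arm and the same true AE risk p in both arms. The reported rate is p × recall.

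- Equal recall of 60%, p = 20%: expected subjects with an event fall from 30 × 0.20 = 6.0 to 30 × 0.20 × 0.60 = 3.6 per arm, with no false difference.
- Unequal recall of 80% and 50%, p = 20%: 30 × 0.20 × 0.80 = 4.8 against 30 × 0.20 × 0.50 = 3.0, a false difference of 0.20 × (0.80 − 0.50) = 6 points.
- The same unequal recall with p from 10% to 30%: 0.10 × 0.30 = 3 points to 0.30 × 0.30 = 9 points.

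For scale, the standard error of the difference between reported rates of 16% and 10% with 30 per arm is √(0.16 × 0.84/30 + 0.10 × 0.90/30) = √0.00748 = 0.086, or about 9 points. The illustrated 6-point bias is smaller than one standard error.

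**The case against.** The strongest reply is that the plan has more than one route for AEs. Observed events are recorded as well as reported ones, pregnancy has its own instruction, and Day 168 carries a full set of examinations and a drug review. A symptom questionnaire also exists. The investigator who grades events and judges causality is stated to be blinded. Section 6.1.3 collects hospitalisation and discharge dates for serious events, and Section 9.2.1 counts hospital records as source data. The study has 60 subjects, uses both drugs on-label, is not powered for clinical endpoints, tests nothing on safety, and has a primary outcome measured by a blinded laboratory operator.

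Most of this stands, and it limits the point. A reader might infer that 97% of exposure rests on a single half-year recall. The documents do not support that: 97% is the share of days without a scheduled contact, not a share of events or of lost events, and the other routes exist. A reader might also infer that the AE comparison is under-counted or biased as a matter of fact. The documents contain no AE or recall rate that could show this, and the recall rates in the illustration are assumed.

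The objection does not close the gap. The other routes are passive, specific to one event, or mainly a picture of Day 168. A blinded investigator cannot grade an event that was never reported. Reporting safety descriptively also does not protect it, because readers will compare raw counts between two arms of about 30.

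**Conclusion.** The point holds as a risk to the completeness and even-handedness of AE collection. Scheduled enquiry is absent for about 163 of 168 treatment days (97%; 94% to 98%), and the stated AE elicitation method at the end of that period is one open question to unblinded subjects. The likely loss is mainly of resolved non-serious events, since deaths and admissions depend less on recall. Unequal reporting between arms is possible, but its size and direction cannot be derived from the documents. The day count rests on Day 5 being the last early review and Day 168 the final visit. The primary result is untouched. This is a worthwhile low-cost improvement to a descriptive safety analysis, not a flaw that undermines the trial.

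**What to change.** In Section 6.2 (Recording of adverse events) and the Section 4 schedule, keep the open question and add a fixed checklist at the existing 6-month visit, worded and administered identically in both arms. It should cover bleeding, breathlessness, syncope or slow pulse, infection, any hospital contact and any new drug. The symptom questionnaire in Section 5.3.1 can serve, with items added where it does not cover these topics, if it is placed in the schedule and positive answers are transferred to the AE Form. Obtain discharge records for each reported admission. State in the report that AEs between discharge and 6 months were collected retrospectively.

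The cost is a one-page form, notice of the amendment to the ethics committee (Section 10.5), and somewhat higher AE counts in both arms. A checklist reduces omission; it does not remove reporting bias from subjects who know their drug.

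Optionally, the existing study nurse (Section 9.1) could make scripted AE and concomitant-drug telephone contacts at intervals the sponsor sets. Two per subject would be 60 × 2 = 120 short calls. They would shorten the recall period and help serious events surface sooner, but the case for the checklist does not depend on them.

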## 6.1.2 Follow-up of unresolved adverse events

Every effort will be made to follow-up and resolve the unresolved AE.

## 6.1.3 Variables

The following variables will be collected for each AE;

- Description of AE.
- The date and time when the AE started and stopped.
- The intensity of the AE according as assessed by study subjects according to the following scale:
  - Mild = awareness of sign or symptom, but easily tolerated
  - Moderate = discomfort sufficient to cause interference with normal activities
  - Severe = incapacitating, with inability to perform normal activities.
- The intensity of the AE assessed by PI as CTCAE grade 1-5.
- Whether the AE is serious or not. The AE assessed by the study subject as severe AE is not equivalent to serious AE.
- Causality assessment in relation to study treatment.
- Action taken with regard to investigational product.
- Withdrawal of the subject from the study due to AE.
- Outcome.

In addition, the following variables will be collected for SAEs:

- Date when AE met criteria for serious AE.
- Date Investigator became aware of serious AE.
- The reason why AE is serious.
- Date of hospitalization.
- Date of discharge or death.
- Probable cause of death.
- Autopsy performed.

#### 6.1.4 Causality assessment

The causality of AE in relation to study treatment will be assessed by the PI, who in completing the relevant AE Report Form will answer ‘yes’ or ‘no’ to the question “Do you consider that there is a reasonable possibility that the event may have been caused by the study medication?” Causality will be assessed using the following definitions:

- Very likely
  - The AE follows a reasonable temporal sequence from study treatment administration;
  - Abates upon discontinuation of study treatment;
  - Reappears on repeated exposure (re-challenge).
- Probable
  - The AE follows a reasonable temporal sequence from study treatment administration;
  - Abates upon discontinuation of study treatment;
  - Cannot reasonably be explained by known characteristics of the subject's clinical state.
- Possible
  - The AE follows a reasonable temporal sequence from study treatment administration, but could have been produced by the subject's clinical state or other mode of therapy administered to the subject.
- Doubtful
  - The temporal association between study treatment and AE is such that the study treatment is not likely to have any reasonable association with the observed event.
- Very unlikely
  - The AE is definitely produced by the subject's clinical state or other mode of therapy administered to the subject.

#### 6.1.5 Disease progression

Not applicable for the purpose of the study.

## **6.2 Reporting of serious adverse events**

Information about all SAE will be recorded on the SAE Form in Investigator's Study File. All events documented in the SAE Form will be reported within 24 hours to the Sponsor (personally or via fax) and to the Office of Medicinal Products, Medicinal Devices and Biological Products (via the online form available at [www.urpl.gov.pl](http://www.urpl.gov.pl)). All SAEs are to be submitted to the AstraZeneca Product Safety mailbox:

[[contact]](mailto:[contact])

## **6.3 Overdose**

A subject with confirmed or suspected overdose of the study medications will undergo thorough clinical and laboratory investigation. In case of any abnormalities upon the investigation, the subjects will be admitted to 1st Chair and Department of Cardiology for further assessment and monitoring.

## **6.4 Pregnancy**

### **6.4.1 Maternal exposure**

The female subject will be instructed to inform the PI if she becomes pregnant during the study and seek advice regarding continuation of the study treatment. The PI will report the pregnancy to the Sponsor within 24 hours of being notified of the pregnancy. The pregnancy will be followed up until the outcome is known.

### **6.4.2 Paternal exposure**

Pregnancy occurring in the partner of a male subject participating in the study will also be will be counselled as described above, reported to the Sponsor and followed up until the outcome is known.

## **6.5 Management of toxicities <<Dose Reductions>>**

A subject with confirmed or suspected toxicity of the study medications will be admitted to 1st Chair and Department of Cardiology for assessment and monitoring. After considering of

benefit to risk ratio the drug will be temporarily withheld. If the toxicity continues after re-initiation of the treatment, the drug will be permanently withheld.

### **6.6.2 Data Monitoring Committee**

There is a Monitoring Committee at the study site which monitors the Investigator's Study File to verify adherence to the protocol and the completeness, consistency and accuracy of the data. The investigator agrees to cooperate with the Monitoring Committee to ensure that any problems detected in the course of these monitoring visits are resolved.

### **6.6.3 Scientific Advisory Committee**

The Scientific Advisory Committee consists of the same members as the Steering Committee excluding PI. The PI will regularly discuss the questionable issues related to the study with the Scientific Advisory Committee.

## **7. INVESTIGATIONAL PRODUCT AND OTHER TREATMENTS**

### **7.1 Identity of investigational product(s)**

Investigational product	Dosage form and strength	Manufacturer
Ticagrelor	Tablets, 90 mg	AstraZeneca
Clopidogrel	Tablets, 75 mg	Synoptis Pharma

## 7.2 Dose and treatment regimens

The investigational product ticagrelor will be administered orally in a loading dose 180 mg, followed by a maintenance dose of 90 mg twice daily for 6 months. Clopidogrel will be administered orally in a loading dose 600 mg, followed by a maintenance dose of 75 mg twice daily.

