### **Investigational product, dosage and mode of administration**

All drugs, including the investigational product ticagrelor, will be administered orally. All subjects will be administered a loading dose of clopidogrel (600 mg) prior to PCI. Subjects randomised to ticagrelor will receive a loading dose of ticagrelor (180 mg), followed by a maintenance dose (90 mg twice daily). Subjects randomised to clopidogrel will continue the treatment with a maintenance dose of clopidogrel (75 mg once daily). According to the guidelines of European Society of Cardiology, double antiplatelet therapy with acetylsalicylic acid (ASA) and a P2Y12 receptor antagonist will be continued for 12 months. The study treatment will last for 6 months until the last visit at the end of the treatment (LSLV). After termination of the study patients will be prescribed double antiplatelet therapy for the remaining 6 months. Ticagrelor will be recommended over clopidogrel. Subjects who choose to switch to clopidogrel due to financial constraints will be prescribed clopidogrel.

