### *Doses*

All drugs will be administered orally, in doses recommended by European Society of Cardiology in the Guidelines on Myocardial Revascularization [3]. If not already administered prior to hospital admission, patients will receive a loading dose of clopidogrel (600 mg) prior to percutaneous coronary intervention (PCI). Patients randomised to ticagrelor will receive a loading dose of ticagrelor (180 mg), followed by a maintenance dose (90 mg twice daily).

Patients randomised to clopidogrel will continue the treatment with a maintenance dose of clopidogrel (75 mg once daily).

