## 7.5 Compliance

Each subject will be dispensed sufficient medication for 24 weeks of therapy. Compliance will be checked by counting of blisters at the last visit at 6 months.

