### 7.7.1 Other concomitant treatment

Subjects will receive a loading dose of aspirin (300 mg) prior to PCI. Unfractionated heparin will be administered during PCI in the dosage left at the discretion of interventional cardiologist. On discharge, all subjects will receive treatment with ASA 75 mg once daily, atorvastatin at least 10 mg once daily, and angiotensin-converting enzyme (ACE)-inhibitor or angiotensin II receptor antagonist (ARB). If indicated, subjects will receive treatment with  $\beta$ -receptor antagonist and mineralocorticoid-receptor antagonist.

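### Section 7.2 gives clopidogrel maintenance as 75 mg twice daily, where the synopsis and Section 1.2 give 75 mg once daily

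*Combined protocol and SAP*

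**What the plan says.** The clopidogrel maintenance dose appears in three readable places.

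- Synopsis, on the investigational product and dosage: control subjects continue on a "maintenance dose of clopidogrel (75 mg once daily").
- Section 1.2, Doses: "Patients randomised to clopidogrel will continue the treatment with a maintenance dose of clopidogrel (75 mg once daily").
- Section 7.2, Dose and treatment regimens: "Clopidogrel will be administered orally in a loading dose 600 mg, followed by a maintenance dose of 75 mg twice daily".

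The sentence before the last of these gives the ticagrelor regimen, "followed by a maintenance dose of 90 mg twice daily for 6 months".

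Section 7.5 makes supply and compliance depend on the regimen: "Each subject will be dispensed sufficient medication for 24 weeks of therapy", and "Compliance will be checked by counting of blisters at the last visit at 6 months". Neither a tablet count nor a compliance formula is given.

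**The concern.** The control arm has two maintenance regimens that differ by a factor of two, and the one that disagrees with the others is in the section devoted to dosing. Three things are at stake.

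- **Dosing safety.** Anyone dispensing or instructing patients from Section 7.2 alone would give twice the clopidogrel dose stated elsewhere, on top of aspirin (Section 7.7.1: "On discharge, all subjects will receive treatment with ASA 75 mg once daily"). The label content listed in Section 7.3 includes neither dose nor frequency, so the box would not correct the error.
- **Late detection.** The schedule in Section 4 has no visit between day 5 and day 168. Section 6.1.1 says that "AE and SAE will be analyzed at each visit during index hospitalization and at the last visit at 6-months", and blisters are counted only at the end. The principal investigator is also meant to be blinded to treatment (Section 3.6).
- **The comparator.** The primary objective compares ticagrelor with clopidogrel, using samples taken on treatment at 48 hours and 6 months (Section 5.7). Until the control dose is settled, the contrast being estimated is not fully defined.

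**Working it through.** The plan has no calculated figure to reproduce here. The check compares the statements and follows each regimen through to supply and compliance.

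**Inputs**

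| Item | Value | Source |
|---|---|---|
| Clopidogrel maintenance | 75 mg once daily | Synopsis |
| Clopidogrel maintenance | 75 mg once daily | Section 1.2 |
| Clopidogrel maintenance | 75 mg twice daily | Section 7.2 |
| Tablet strength | 75 mg | Section 7.1 |
| Length of supply | 24 weeks | Section 7.5 |
| Last two scheduled days | 5 and 168 | Section 4 |

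**Step 1: daily dose.** Dose × frequency.
- Synopsis and Section 1.2: 75 × 1 = 75 mg/day.
- Section 7.2: 75 × 2 = 150 mg/day.
- Ratio: 150 / 75 = 2.

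**Step 2: tablets per control subject.** Days × tablets per day, with 24 × 7 = 168 days.
- Once daily: 168 × 1 = 168 tablets.
- Twice daily: 168 × 2 = 336 tablets.

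**Step 3: what happens if different staff use different sections.** These are alternative scenarios and cannot both apply to one patient.
- Supply set for once daily, patient told twice daily: 168 / 2 = 84 days, so the tablets run out at week 12 of 24.
- Patient takes once daily with full adherence, count judged against Section 7.2: 168 / 336 = 50% apparent compliance. Protocol non-compliance is a ground for discontinuation and withdrawal (Sections 3.9 and 3.10), and withdrawn subjects are replaced.

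**Step 4: time without a scheduled check.** 168 − 5 = 163 days.

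**Step 5: which dose was meant.** Four points favour once daily:
- Two of the three statements give it.
- Section 1.2 says the doses are those the European cardiology guideline recommends, and then gives once daily.
- The benefit/risk text in Section 1.2 says that all study drugs are used on-label.
- The odd statement directly follows a ticagrelor sentence containing the same frequency, so carry-over is a natural explanation.

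Nothing readable supports twice daily apart from the sentence in Section 7.2.

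**The case against.** The best case on the other side is that this is a small editorial slip. The intended dose is clear from the two consistent statements and from the guideline and on-label clauses, and cardiology staff would probably recognise the error. Figure 1 is not visible in the text available. Its legend defines both once-daily and twice-daily abbreviations, so the figure may state the dose correctly. Patients are encouraged to report adverse events to the investigator between visits (Section 10.4), and the protocol provides for work-up of suspected overdose or toxicity. The run-out and 50% compliance figures need particular mismatches between sections. The documents give no bleeding risk or dose limit for 150 mg/day, so the degree of harm is not quantified.

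Much of this stands. The intent is fairly clear, the scenarios are conditional, and the size of any harm cannot be taken from the documents. Reporting between visits is a real but partial safeguard, since it depends on a symptom or a suspicion arising. None of it removes the conflict: whatever Figure 1 shows, the text of Section 7.2 would still contradict the synopsis and Section 1.2. These points make harm less likely, but they do not justify leaving a two-fold dose conflict in the section that prescribes treatment.

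**Conclusion.** The concern holds. Section 7.2 is wrong as written or, much less likely, the synopsis and Section 1.2 are. The certain size is 150 against 75 mg/day, and 336 against 168 tablets per control subject over 24 weeks. The day-84 run-out and the 50% apparent compliance follow only if supply, instructions and counting are taken from different sections.

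This must be fixed because the error concerns dose and stands in the operative regimen section. The conclusion assumes that Section 7.2 could be used on its own for dispensing or instruction. Nothing in the documents shows that any patient was misdosed, and no sample-size, power or significance figure is affected.

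**What to change.** Change the clopidogrel maintenance frequency in Section 7.2 to once daily, to match the synopsis and Section 1.2. Only if the sponsor confirms that twice daily was intended should those two places be corrected instead.

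In Section 7.5, base the dispensed quantity and the blister-count denominator on the same regimen: 168 tablets of 75 mg per control subject at once daily. Check that Figure 1 agrees.

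Notify the ethics committee, as Section 10.5 already provides. The cost is a one-line protocol correction and the notification, with no extra patients, visits or procedures.
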